*****Protection against risks of medications*****

Effective screening will exclude participants who would be at greater risk for complications because of medical, neurological or psychiatric illnesses. Individuals currently dependent on other drugs will be screened out. Participants will be carefully monitored during each human laboratory session and will be given only single, observed doses of study medications. Participants will be educated of the risks attendant to study participation through the informed consent process.

Protection Against Risks of Lacosamide

Participants will take lacosamide only in an observed single dose administration by research staff. They will then be monitored closely from the time of medication administration at 8:30 until leaving the CRC at 8:00 PM.

Protection Against Effects of Lacosamide on Other Medications

To protect against this risk, we will do the following:

-The study physician will review all concomitant medications and determine whether there are potential drug interactions that need to be avoided.

-In the informed consent form, participants are instructed, "Lacosamide may cause a change (increase or decrease) in the effect of some other medications. If you are taking other medications during your participation in this study, immediately inform study staff. The study doctor will review any medications that you are taking and make the determination as to whether continued study participation is safe for you."

Blood Drawing (Venipuncture) Risks

Participation in the study requires participants to have their blood drawn 4 different times over the course of study (screening and human laboratory ADP sessions 1, 2, and 3). Having blood drawn may cause pain (common), fainting/passing out (not very often), a bruise where the needle goes in (not very often), and infection at the same place (rare).

*****Protection against blood drawing (venipuncture) risks*****

To protect against this risk, we will do the following:

- 1) Professionally trained phlebotomists at the CTSI Clinical laboratory will perform all phlebotomies.

Risk of Privacy/Confidentiality

Participation in the study presents a risk to the participant of loss of privacy and confidentiality regarding research material, particularly with respect to potentially embarrassing or harmful personal health information, particularly related to mental health and alcohol and substance use. This includes detailed and sensitive information regarding alcohol and drug use, and psychiatric symptoms. For example, urine drug testing will be conducted. Potential release of information regarding drug use, in particular, could have serious implications if made known, for example legal ramifications, jeopardizing insurability or employability.

In order to ensure the safety of the participant and others, information may be shared between research staff and the clinical team only under the following circumstances: 1) If in the judgment of the study physician, the participant has a psychiatric or medical condition that requires urgent attention to protect the safety of the participant or others; and 2) If a participant has missed several study appointments, and research staff needs to verify the participant's whereabouts and/or verify the participant's safety. These above circumstances will be clearly outlined in the informed consent form, and be discussed and clarified with prospective participants at the start of the study.

*****Protection against risks to privacy/confidentiality*****

To protect against this risk, we will do the following:

- In the informed consent form, participants are instructed: "Participation in research may involve a loss of privacy, but information about you will be handled as confidentially as possible. If you do not already have a medical record at the VA Medical Center, San Francisco, one will be created because of your participation in this study."
- *HIPAA regulations will be followed throughout this study. Several methods* will be used to decrease the risk of loss of confidentiality to participants.
 - First, all study forms will be labeled with a unique, identifying code number, and maintained in a locked cabinet. Those that contain the names of participants or other identifying information will be stored in a locked cabinet, separate from other study forms.
 - Second, research material will not be shared between the research team and clinical staff - with the exception of information to be shared only to ensure the safety of the participant and others.

- Third, no names will be used in any published reports about this study.
- Fourth, most of the questionnaire data will be collected using an online survey instrument called Qualtrics: All collected research data will be referenced by unique study identification codes only, stored in an electronic database (SQL server) on a password-protected secure VA server behind a secure VA firewall at SFVAMC available to study staff only. After receiving CHR and R&D approval, we will be collecting most of our questionnaire measures in digital format, so that this questionnaire data can be collected using an online survey instrument called Qualtrics, which meets strict IRB and HIPAA data security requirements. Data will be entered into SQL Server tables using MS Access as a front-end or batch load from an external file. At a point of entry, form values are subjected to consistency edit checks (e.g. range and type verification, missing data). Scoring algorithms are applied where appropriate. Once data is entered into the database, edit checks are run for accuracy.

Unknown Risks

Participants may experience side effects that are not known yet.

******Protection against unknown risks******

To protect against this risk, we will do the following:

- During the informed consent process, participants will be notified about the possibility of unknown risks associated with taking lacosamide or their combination with alcohol.
- During the informed consent process, the possibility of unknown risks are explained and that researchers will let participants know if new information about risks and side effects becomes available over the course of the study.
- Adverse effects will be carefully monitored during each ADP lab session.

4. STUDY OBJECTIVES

4.1 Hypothesis

Include a clearly defined hypothesis, if relevant, and list the key questions the study is expected to answer. Be detailed, clear and as specific as possible.

4.2 Primary Objective

As this is a small pilot study, the Primary Aims are *process*- rather than *outcome*-oriented:

1. To establish the feasibility and safety of giving lacosamide to human participants in a laboratory alcohol self-administration procedure; and
2. To allow our research team to gain experience with these procedures and fine-tune them.

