2. BACKGROUND

2.1 Background Prevalence of Research Topic

AUD is difficult to treat, and currently available medications are underutilized, due at least in part to their limited effectiveness [1-3]. There is a critical need for more efficacious medications for AUD. Preclinical rodent work from ACGT investigator [name] has identified a specific molecular target that promotes excessive alcohol intake. [name] discovered that *collapsin response mediator protein-2 (CRMP-2)* [4], a downstream mediator of *mammalian target of rapamycin complex 1 (mTORC1)* signaling [4-8], is critical for promoting excessive alcohol intake [4].

The central goal of this pilot project is to lay down the groundwork necessary for the later conduct of more definitive studies designed to translate the ACTG's basic science discoveries into human trials of novel pharmacotherapies for AUD. The FDA-approved anticonvulsant, lacosamide [13,38-40] inhibits CRMP-2 [4,12,13]. We will conduct the first pilot laboratory clinical trial of lacosamide in humans with AUD. The ultimate goal of this proposal is that this medication can be repurposed for the treatment of AUD if it is safe and feasible to use in future larger studies that will test its ability to reduce alcohol drinking and behavioral biases for alcohol in heavy drinkers with AUD.

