Even though participants will be exposed to only a single dose of lacosamide, it has been noted that "all antiepileptic drugs including lacosamide increase the risk of these thoughts or behaviors in patients taking these drugs for any indication"¹³. An FDA Alert, updated 12/16/2008, (US Food and Drug Administration 2008) 11 antiepileptic or anticonvulsant drugs associated with: "reports of suicidality (suicidal behavior or ideation [thoughts])...FDA is requiring ... that all manufacturers of drugs in this class include a Warning in their labeling.... FDA's pooled analyses of 199 clinical trials of eleven antiepileptic drugs... showed that patients who received one of the antiepileptic drugs had almost twice the risk of suicidal behavior or ideation (0.43%) compared to patients who received placebo (0.24%). This... represents the occurrence of approximately one additional case of suicidal thinking or behavior for every 530 patients treated with an antiepileptic drug... The increased risk was observed as early as one week after starting treatment and throughout the observed duration of treatment. The increased risk of suicidal thoughts or behavior was generally consistent among the eleven drugs with varying mechanisms of action and across a range of indications. This observation suggests that the risk applies to all antiepileptic drugs used for any indication...."

Dizziness and ataxia

The package insert notes this as a warning/precaution¹³. See above for incidence of these adverse effects. At the doses that we will be using, dizziness and ataxia could be expected to occur in 16% and 4% of participants, respectively, and may be increased by combining lacosamide with alcohol.

Cardiac rhythm and conduction abnormalities

The package insert notes this as a warning/precaution¹³. It is recommended that an ECG be obtained before starting lacosamide and that other medications that could prolong PR interval be avoided.

Syncope

Although listed as a warning/precaution¹³, the package insert notes that there was no increase in syncope compared to placebo in epilepsy patients with no significant system illnesses.

Controlled substance

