5.3.1 Number of Participants

The study will enroll 4 men participants. We anticipate needing to start up to 6 participants to get 4 to complete all 3 human lab sessions.

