6.1.2 Dosage, Admin, Schedule

The manufacturer for lacosamide (LAC) (Vimpat®) has no involvement with the study. The Wellspring Compounding Pharmacy (WCP) in Oakland, CA is selected by the SFVAMC Research Pharmacy to compound placebo-controlled medications. WCP will obtain LAC from the manufacturer, and prepare 100 mg of LAC, 200mg capsules of LAC, and matching placebo. The SFVAMC Research Pharmacist will directly receive all study medications from WCP and store

appropriately. A single dose of either LAC 100 mg, LAC 200 mg or matching placebo will be given in each of the 3 Human Lab Sessions.

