6.4.1 Statistical Design

As this is a pilot feasibility study, no inferential statistics will be used.

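### Primary aim 1 is worded to establish feasibility and safety, but 4 to 6 men summarised by central tendency and variability cannot support that verb, and the summaries hide how uncertain a clean result would be

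*Combined protocol and SAP*

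**What the plan says.** Section 4.2 opens with a qualifier, "As this is a small pilot study", and describes the primary aims as concerned with process and not outcome. Aim 1 then reads "To establish the feasibility and safety of giving lacosamide to human participants in a laboratory alcohol self-administration procedure". Aim 2 is about gaining experience with the procedures. The secondary aim in section 4.3 is worded more cautiously, as a preliminary assessment.

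On numbers, section 5.3.1 says "The study will enroll 4 men participants" and adds "We anticipate needing to start up to 6 participants to get 4 to complete all 3 human lab sessions". The design is a crossover, and section 6.1.2 states "A single dose of either LAC 100 mg, LAC 200 mg or matching placebo will be given in each of the 3 Human Lab Sessions". Each completer therefore contributes one session at each lacosamide dose and one on placebo.

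On analysis, section 6.4.1 says "As this is a pilot feasibility study, no inferential statistics will be used". Sections 6.4 and 6.4.3 plan measures of central tendency and of variability. Section 6.4.2 treats sample size as not applicable. Retention by stage and adverse effects by condition are primary outcomes (5.2.1, 6.4.3.1), and section 6.4.3.3 gives the safety analysis as descriptive. No interval estimate is planned, and no retention level or adverse-event rate is named as the mark of feasibility or safety.

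Two further statements give context. Section 2.1 speaks of repurposing the drug "if it is safe and feasible to use in future larger studies". Section 3.3.2, under dizziness and ataxia, says that at the study doses "dizziness and ataxia could be expected to occur in 16% and 4% of participants", and that alcohol may increase these effects.

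**The concern.** To establish safety is to reach a conclusion. Four to six men with bare descriptive summaries cannot support one, and the planned summaries do not show a reader how far short they fall. A mean and standard deviation of a yes/no outcome carry no sign of uncertainty when nobody, or everybody, has the outcome.

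What is at stake is how the result is read later. Sections 3.3.2 and 6.1.1 say that no human data on lacosamide with alcohol have been published, so planners of the next study may lean on whatever this pilot reports. A run with no events and full retention, set beside an aim worded in this way, could be taken as stronger evidence than it is.

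**Working it through.** The plan states no rate, margin, confidence level or sample-size derivation, so there is no figure of its own to reproduce. The 95% level below is an assumption.

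**Inputs**
- Men per condition: 4 completers, at most 6 if every man started is dosed in that condition (5.3.1).
- Expected rates: dizziness 16%, ataxia 4% (3.3.2).

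**1. What the planned variability measure shows.** For a yes/no outcome with observed proportion p, the standard deviation is proportional to √[p(1 − p)]. At 0/4, p = 0 and at 4/4, p = 1. Both give exactly 0.

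**2. Upper limit for an event not seen.** The exact (Clopper-Pearson) two-sided 95% upper limit for 0 in n is 1 − 0.025^(1/n).
- 0/4: 1 − 0.025^(1/4) = 1 − 0.398 = 60.2%.
- 0/6: 1 − 0.025^(1/6) = 1 − 0.541 = 45.9%.

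Other conventions for 0/4:

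| Method | Upper limit |
|---|---|
| Agresti-Coull, 95% | 54.6% |
| Exact, one-sided 95% | 52.7% |
| Wilson, 95% | 49.0% |
| Jeffreys, 95% | 44.5% |

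Every version lies far above 16%. Counting the 8 active-drug sessions as 0/8 would give 1 − 0.025^(1/8) = 36.9%, but those are repeated sessions in the same 4 men and are not independent.

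**3. Retention.** The exact 95% lower limit for 4/4 is 0.025^(1/4) = 39.8%, so the interval is 39.8% to 100%. For 4/6 it is 22.3% to 95.7%.

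**4. Chance of seeing no case at the protocol's own rates,** (1 − rate)^n:
- Dizziness, 4 men: 0.84^4 = 0.498. With 6 men: 0.84^6 = 0.351.
- Ataxia, 4 men: 0.96^4 = 0.849. With 6 men: 0.96^6 = 0.783.

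If alcohol raises the rates, these chances fall. As an illustration only, doubling dizziness to 32% gives 0.68^4 = 0.214, so about one such study in five would still show no case in 4 men.

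**5. Scale.** With no events, an exact two-sided 95% upper limit at or below u needs n ≥ ln(0.025)/ln(1 − u). That is 11 men for 30%, 17 for 20% and 36 for 10%. This shows the distance between the verb and the design. It is not a call for a larger pilot.

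**The case against.** The best defence is context. The sentence introducing the aims calls the study a small process-oriented pilot, section 6.2.1 says it is not an efficacy study, and section 2.1 describes groundwork for more definitive work. Read in that light, aim 1 means showing that the procedure can be run while watching for harm. Leaving out inference is a disclosed choice with a stated reason, applied consistently. Counts in four men are transparent, and an interval for every checklist item, by condition and before and after alcohol, would produce many wide and near-identical ranges.

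Much of this stands, and it limits the point. A reader might infer that a clean run will be declared safe, or that these four men decide whether larger studies proceed. The documents do not say so: no rule turns 0/4 into a safety conclusion, and the phrase in section 2.1 is a condition within an ultimate goal, not a go/no-go rule.

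A reader might also infer that participants are left unprotected. That is not supported either. Dosing is single and observed, with monitoring until discharge (3.3.2), and a monitoring board, a medical monitor and a halt after a related serious event are in place (7.4, 7.5).

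The 60% figure also depends on method and denominator, and the 16% and 4% rates come from adjunctive epilepsy treatment at 100 mg twice daily, not from single doses.

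What the defence does not answer is narrower. Adverse effects by condition are a primary outcome, so safety is part of what the study reports. The secondary aim shows that the authors had more cautious wording to hand. And a variability measure that equals zero at 0/4 or 4/4 is a poor summary even of a pilot.

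**Conclusion.** The point holds as a matter of wording and reporting. Aim 1 claims more than the design can conclude, and the planned summaries hide the uncertainty just where it is largest. The size is an upper limit of 60% for 0/4 (46% for 0/6, and about 45% to 55% for 0/4 under other conventions) and a retention interval of 40% to 100% for 4/4. The chance of missing dizziness or ataxia altogether in 4 men is up to about 50% and 85%.

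These results rest on a 95% level, on independent men, on a fixed number of men in each denominator, and on true rates at least as high as those the protocol quotes. The documents do not say how single dosing would shift those rates. None of this is a calculation error, a failure of participant protection, or a reason to change the number of participants.

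**What to change.** - In section 4.2, reword aim 1 as obtaining preliminary data on the feasibility and tolerability of lacosamide in the self-administration procedure.
- In section 6.4.1, allow interval estimation while still excluding hypothesis tests.
- In sections 6.4.3.1 and 6.4.3.3, report counts with exact (Clopper-Pearson) 95% intervals for retention at each stage and for a short list of adverse effects in each condition: any adverse effect, dizziness and ataxia. Three outcomes in three conditions make 9 safety intervals. Remaining checklist items can stay as counts.
- Define the safety denominator as all men dosed in that condition, and do not pool sessions as if they were independent.
- State that no events in 4 to 6 men does not exclude common events.

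The cost is a few sentences and a few lines of analysis code, with no added participants, visits or procedures. The price is wide published intervals and a more modest stated conclusion.

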4.3 Secondary Objectives

The Secondary Aim is to obtain a preliminary assessment of the effects of lacosamide on alcohol consumption and related behaviors in individuals with AUD.

5. STUDY DESIGN

5.1 General Design

We will conduct a double-blind, placebo-controlled, within-subjects pilot laboratory trial. Four heavy-drinking, non-treatment seeking community volunteers with AUD will each undergo 3 ADP human laboratory sessions. They will be randomly assigned to receive a single dose of either 1) lacosamide 100 mg, 2) lacosamide 200 mg, or 3) placebo, in a balanced crossover design, in each of 3 human laboratory sessions, with 1 week between sessions. In each session, 2 hours after medication administration, participants will undergo a series of tests (impulsivity, craving, alcohol approach-avoidance task, and as a control measure, a reaction time task (the *Digit Vigilance Test*), followed by a priming drink and two alcohol self-administration periods, using the ADP.

5.1.1 Study Duration

The study begins with a screening visit that is expected to last approximately 3 hours. If it is deemed safe for the participant to enroll in the study and they meet all eligibility criteria, then the participant will be scheduled for 3 human lab sessions, each 12 hours long. The human lab sessions will take place on separate weeks with at least 7 days, or a washout period, before the next human lab session can commence. A follow-up visit will be scheduled at least 7 days after the 3rd and final human lab session.

5.2 Outcome Variables

This section describes the primary and secondary outcome variables, which are the endpoints that will be used to assess the study.

5.2.1 Primary Outcome Variables

The primary outcome variables are measures of feasibility:

1. Time needed to recruit, screen, and run the study procedures for 4 participants.
2. Retention rates at the various in the study process (screening, Human Lab ADP session 1,2,3, and follow-up).
3. Adverse effects of study medication (lacosamide at 2 doses and placebo), before and after alcohol self-administration.

5.2.2 Secondary Outcome Variables

Secondary outcomes:

1. Alcohol craving
2. Alcohol consumption during each of the 3 Human Lab ADP sessions.
3. Alcohol – medication interaction effects on BAES, DVT, MD gait and body sway check, Alertness VAS and computer tasks (AAT, BART, and DD)

5.3 Study Population

A total of 4 male non-treatment seeking healthy community volunteers will be enrolled.

5.3.1 Number of Participants

The study will enroll 4 men participants. We anticipate needing to start up to 6 participants to get 4 to complete all 3 human lab sessions.

5.3.2 Eligibility Criteria

Inclusion Criteria:

1. Men, ages 21-50;
2. Able to read English and to complete study evaluations;
3. Meet DSM-V criteria for current alcohol use disorder (AUD);
4. Average weekly alcohol use of 25-70 standard drinks for men over the past 30 days;
5. No more than an average of 3 days/week of alcohol abstinence in the past 30 days, to maximize likelihood that participants will choose to drink during the laboratory sessions.

Exclusion Criteria:

[figure not shown]
1. Individuals who are seeking AUD treatment or have been in treatment within the past 6 months;
2. Current DSM-V non-alcohol substance use disorders other than tobacco and cannabis;
3. Positive urine drug test results at more than one screening appointment for opioids, cocaine, benzodiazepines, or barbiturates;
4. Regular use of psychoactive drugs including antipsychotics, anxiolytics and antidepressants during the 30 days prior to entry, as well as regular use of anticonvulsants, beta blockers, central nervous system stimulants or depressants, or other drugs that cause excessive sedation;
5. Taking medications that may interact with lacosamide, e.g. medications that prolong the ECG PR interval, or medications with strong CYP3A4 and CYP2C9 inhibition;
6. Psychosis or any other serious mental illness as judged by SCID and study physician assessment;
7. Medical conditions that in the judgment of the study physician contraindicate the consumption of alcohol;
8. Medical conditions that in the judgment of the study physician contraindicate LAC (no contraindications listed in the FDA-approved Prescribing Information for LAC);
9. Any other medical conditions that in the opinion of the study physician would make study participation hazardous;
10. History of serious alcohol withdrawal (e.g. seizures, DTs, hospitalization) or a Clinical Institute Withdrawal Assessment Scale (CIWA-AD) score ≥ 8 ;
11. Participants who report disliking spirits will be excluded because 80 proof liquor will be provided during the alcohol self-administration periods;
12. Participants who have taken any investigational drug within 4 weeks preceding study entry.

13. Participants with first-degree atrioventricular block (AV block), PR interval lengthened beyond 0.20 seconds, or greater.

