6.1.6 Concomitant Therapy

Participants will be informed that they cannot use psychoactive drugs including antipsychotics, anxiolytics and antidepressants during the 30 days prior to entry, as well as anticonvulsants, beta blockers, central nervous system stimulants or depressants, or other drugs that cause excessive sedation in the judgment of the study physician/PI.

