- ECG: an electrocardiogram will be performed to check cardiac conduction, in particular for PR interval prolongations, as this is of relevance to LAC, which can cause small, dose-related increases in mean PR interval
- Structured Clinical Interview for DSM-5, (SCID) [96]: the SCID will be used to determine DSM-V diagnosis of current (current year) Alcohol Use Disorder, and the DSM-V current psychiatric diagnoses for anxiety, mood, psychotic, and non-alcohol substance use disorders in order to determine study eligibility.
- Alcohol Use Disorders Identification Test (AUDIT): The AUDIT [97] is valid and reliable self-report measure of alcohol-related problem severity.
- Barratt Impulsiveness Scale (version 11) (BIS-11) [98]: This provides a trait measure of impulsiveness and will be used to characterize the study cohort at study entry.

- **Study Physician Review:** All health measures, medical history/exams and labs will be reviewed by a study physician to ensure that the subject meets all the eligibility criteria and are ready for randomization

At Entry and at various times throughout the study:

- **Clinical Institute Withdrawal Assessment for Alcohol, DSM-IV Version (CIWA-AD):** at entry and before each Human Lab Session and at each Follow-up;
- **Urine Drug Screen:** For opioids, benzodiazepines, cocaine, amphetamines, barbiturates: at entry and before each Human Lab Session;
- **Breath alcohol concentration (BrAlc):** at entry and before each Human Lab Session; and during each Human lab Session
- **Vital Signs:** Temperature, heart rate, and blood pressure will be measured at study entry and multiple times during each Human Lab Session.
- **Concomitant Medications Review:** at entry and before each Human Lab session: thorough review of all concomitant medications (prescription or over-the-counter) in the past 30 days, as well as those started during the study.
- **AE Checklist:** At Entry and at Human Lab Session 1, 2 and 3; Phone visits 1, 2, 3; 1-wk FU; The most commonly experienced side effects listed in the FDA package insert will be reviewed. Participants will be asked how many times they have experienced each side effect since the last study visit and severity.

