- **Timeline Followback (TLFB):** at study entry, then Human Lab Session 1, 2 and 3; phone visits 1, 2 and 3. TLFB will be used to calculate standard drinks consumed per week in the past 30 days prior to consent and at the two Human Lab Sessions, and the 1-week follow-up. The TLFB will be used to determine whether subjects meet minimum alcohol consumption criteria at entry. Other substance use will also be collected by TLFB.
- **Balloon Analogue Risk Task (BART):** at each Human Lab session after medication
- **Delay Discounting:** at each Human Lab session after medication

At Follow-up visit:

- **Medical Management:** at the follow-up visit, research clinician will provide a motivational enhancement session to encourage the non-treatment seeking participants to consider treatment.

Measures of Alcohol Effects:

- **Breath alcohol concentration (BrAlc) [99] *at each visit, and multiple times in ADP Sessions 1 and 2.*** BrAlc will be measured at each session to detect recent alcohol use with the *Intoximeters Alco-Sensor IV* instrument.
- **Blood Alcohol Levels:** Human Lab Sessions 1 and 2 (Table 1): Blood samples will be drawn to measure plasma levels of blood alcohol (BAC) during the priming dose and during the alcohol self-administration paradigm. Blood samples will be stored at -4°C and will be analyzed at the San Francisco VA.
- **Biphasic Alcohol Effects Scale (BAES) [81]:** Human Lab Sessions 1 and 2 (Table 1). This 14-item self-report rating scale measures alcohol stimulant/ sedative effects and is used regularly in the Yale ADP.
- **Alcohol Urge Questionnaire (AUQ):** At study entry; multiple times in Human Lab Sessions 1 and 2 (Table 1); 1-wk FU; 1-mo FU: The AUQ is an 8-item questionnaire assessing *desire, expectation of positive effect, and inability to avoid drinking if alcohol is available.* The AUQ is a reliable and valid scale for the measurement of self-reported alcohol urges. Its brevity and time frame for ratings (i.e. right now) makes it suitable for the ADP.
- **Yale Craving Scale -Short (YCS):** Multiple times in Human Lab Sessions 1 and 2; visual analog scale that measures craving for alcohol

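### Exclusion 3 leaves out amphetamines, one of the five drug classes that the urine screen tests, so repeated amphetamine-positive screening tests do not meet it

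*Combined protocol and SAP*

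**What the plan says.** Exclusion 3 (section 5.3.2) is the only eligibility criterion that names a urine result. It excludes men with "Positive urine drug test results at more than one screening appointment for opioids, cocaine, benzodiazepines, or barbiturates".

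The description of the urine drug screen in section 6.3.5 gives a longer list: "For opioids, benzodiazepines, cocaine, amphetamines, barbiturates: at entry and before each Human Lab Session".

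Other text also bears on stimulants:

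- Exclusion 4 (section 5.3.2) covers psychoactive drugs "as well as regular use of anticonvulsants, beta blockers, central nervous system stimulants or depressants".
- Exclusion 2 (section 5.3.2) covers "Current DSM-V non-alcohol substance use disorders other than tobacco and cannabis".
- Section 6.1.6 says that participants will be told they cannot use certain drugs, among them "central nervous system stimulants or depressants, or other drugs that cause excessive sedation in the judgment of the study physician/PI". The word *regular* does not appear there.
- Section 3.3.2, on protection against medication risks, states: "Individuals currently dependent on other drugs will be screened out".
- Section 6.3.5 adds, for the Timeline Followback (TLFB): "Other substance use will also be collected by TLFB". It also has a study physician review history, examinations and laboratory results against the eligibility criteria before randomization.

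On the number of screening visits, section 6 (step 3) and section 6.3.3 allow one or two. The schedule in section 6.3.1 lists one.

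**The concern.** The protocol means to keep stimulant users out. It lists cocaine in exclusion 3, restricts central nervous system stimulants in exclusion 4 and section 6.1.6, and pays for an amphetamine test. But the one criterion that turns a urine result into an eligibility decision skips that class. Where the protocol wants an exemption it names it, as exclusion 2 does for tobacco and cannabis. No such statement is made for amphetamines, so the omission looks like a drafting slip.

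What is at stake is who enters a very small study. Adverse effects are a primary outcome (section 5.2.1). The secondary outcomes (section 5.2.2) include craving, alertness, digit vigilance and the impulsivity tasks, and vital signs are used to examine safety (section 6.3.5). A participant's stimulant use could plausibly bear on all of these. The gap also leaves staff without a written rule when an amphetamine-positive result comes back.

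**Working it through.** No figure in the plan is to be reproduced and no statistical calculation applies. The check compares two lists and then follows cases through the criteria.

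**Step 1. Compare the lists.**

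| Class | Panel (6.3.5) | Exclusion 3 (5.3.2) |
|---|---|---|
| Opioids | yes | yes |
| Cocaine | yes | yes |
| Benzodiazepines | yes | yes |
| Barbiturates | yes | yes |
| Amphetamines | yes | no |

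The panel has 5 classes and exclusion 3 has 4; 5 − 4 = 1, and the one is amphetamines.

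**Step 2. Look for another rule that acts on the amphetamine result.** Exclusion 2 needs a current use disorder, which section 6.3.5 establishes by structured interview. Exclusion 4 needs regular use; it defines no threshold and names no source of evidence. Section 6.1.6 is information given to participants and states no eligibility consequence; section 6.1.7 only refers back to the exclusion criteria. The physician review applies the criteria as written. None of these says what an amphetamine-positive test means.

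**Step 3. Follow cases through the text.**

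| Case | Exclusion 3 as written | Exclusion 3 with amphetamines added |
|---|---|---|
| Two screening visits, cocaine-positive at both | met | met |
| Two screening visits, amphetamine-positive at both | not met | met |
| Two screening visits, positive at one only, any class | not met | not met |
| One screening visit, positive for any class | cannot be met | cannot be met |

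In every row where exclusion 3 is not met, the man is kept out only through exclusion 2 or 4, or another criterion unrelated to the test. Row 2 is the effect of the missing word. Row 4 is a second fault in the same sentence: positives at more than one appointment need at least two appointments, while sections 6 and 6.3.3 allow one and section 6.3.1 schedules one. For a man screened in a single visit, the criterion does nothing for any of the five classes.

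**Step 4. Scale.** One man is 1/4 = 25% of the four planned completers and 3 of 4 × 3 = 12 completed sessions. If six are started (section 5.3.1), he is 1/6, or about 17%, of those started. These are the shares of any one participant. They do not say how likely such a man is to be screened or to pass the other criteria, and the documents give no figure for that.

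**The case against.** The strongest reply is that stimulants are already covered. Exclusion 4 bars regular use and exclusion 2 bars a use disorder. Section 3.3.2 says that dependent individuals are screened out, TLFB collects other substance use, and a physician reviews the laboratory results before randomization. Nothing stops that physician from reading two amphetamine-positive urines as evidence of regular use.

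Much of this stands, and it rules out two stronger readings. A reader might infer that a man with repeated amphetamine positives enters the study. The documents do not support that: failing to meet exclusion 3 is not the same as being eligible. A reader might also infer that the amphetamine test can exclude nobody. That too goes beyond the text, because exclusion 4 does not limit what evidence may be used.

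The reply does not make the mismatch harmless, however. Exclusions 2 and 4 overlap with exclusion 3 for the other classes as well, through use disorders and regular use of stimulants or depressants. The protocol still wrote a urine rule for those four. If the overlap were sufficient, exclusion 3 would not be needed at all. A man with repeated positives who reports occasional use and has no use disorder is left to an undefined word.

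A second reply is that stimulant use on some lab-session days and not others would be the more damaging problem in a within-subject design, and a screening criterion cannot prevent it. That is correct. The screen is repeated before each session, but no section ties a session-day result, for any class, to a stated action. The change proposed here leaves that as it is.

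A third reply is that little hangs on it statistically: primary outcomes are feasibility measures and section 6.4.1 rules out inferential statistics. That also stands and limits the weight of the point.

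**Conclusion.** The point holds in a limited form. The panel and exclusion 3 differ by exactly one class, amphetamines, without explanation and against the direction of exclusion 4 and section 6.1.6. An amphetamine-positive result therefore has no stated eligibility consequence of its own. Whether such a man is kept out depends on a judgment of regular use or of a use disorder.

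The effect is modest. No test or efficacy conclusion is at risk, other criteria partly close the gap, and the share of one man in four describes the size of the study and is not an estimate of bias. The conclusion assumes that the omission is unintended, since no section gives a reason for it. It is worth correcting because the correction is nearly free and the same sentence has a wider fault: with a single screening visit, exclusion 3 cannot be met for any class.

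**What to change.** 1. Add amphetamines to exclusion 3 in section 5.3.2 so that it lists the same five classes as the panel in section 6.3.5. If the omission is intended, give the reason and say how an amphetamine-positive result bears on exclusion 4.
2. Reconcile the requirement for positives at more than one screening appointment with the one or two visits in sections 6 and 6.3.3 and the single visit in section 6.3.1, so that the criterion can operate for everyone who is screened. Without this, the first change has no effect on a man screened in one visit.
3. While the text is open, align exclusion 4 with section 6.1.6 on whether any use or only regular use of central nervous system stimulants is meant.

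The amphetamine test is already performed, so the first change costs one word and possibly one more screen failure. The second is also a text edit; if it is settled by requiring two appointments, it adds a visit for men who would otherwise have had one.
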